Recent literature has found that burnout is highly prevalent among healthcare professionals, affecting between 40-60% of physicians. [1] The added stressors of the COVID-19 pandemic have also been associated with high rates of multidisciplinary healthcare professional burnout, depression and anxiety, especially among women, nurses, and those working in hospital environments.[2-3] Mental health disorders are also prevalent among health care workers. In a study of 4833 physicians, 41.7% screened positive for depressive symptoms and 6.9% reported having suicidal ideation in the previous year, of whom 27% reported that they would probably or definitely not seek help.[4] The healthcare professionals most in need of care and burnout prevention modalities are those least likely to seek support, with a perceived stigma associated with seeking help.[5] These findings contribute to the mounting body of evidence suggesting there is a significant unmet gap in this vulnerable population.

Healthcare clinicians work in a high-stress environment that requires quick decision making and high levels of both mental and physical acuity. Like other performance careers, a clinician's own mental and physical states are key to their ability to take optimal care of their patients. However, despite the

Last Updated: 2.24.2023

similarities shared with these other performance careers, performance coaching, well-being interventions, and other burnout prevention initiatives are commonly perceived as either ineffective, or out of reach to the health professional workforce due to time restraints, lack of knowledge, or pre-existing stigmas around help seeking. Arena Strive and WHOOP aim to address these barriers by democratizing performance coaching with a seamless asynchronous coaching experience at the clinicians fingertips.

METHODOLOGY

Study design

This study is a prospective randomized controlled longitudinal crossover design with a per protocol analysis integrating one sensor (WHOOP, inc Platform) and one educational intervention (Arena Strive Platform). The **WHOOP** sensor collects **data** on heart rate (HR), heart rate variability (HRV), and sleep data, and will be worn by all participants in the experimental intervention. Participants will be asked to wear the biometric sensor for 12 weeks but will have optional access to the device for a total of 24 weeks.

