Participants sought for this study will include full time Physicians and Advanced Practice Providers employed by Atrium Health Sanger Heart and Vascular Institute, Surgery, Emergency Department, and Pulmonary Critical Care. Investigating this special subject population will allow the study team to address with the greatest accuracy the effects of the proposed intervention on the unique workforce at Atrium Health. The maximum number of subjects sought for this study is 100; with a 2:1 randomization ratio with 2/3 receiving the experimental intervention, and 1/3 receiving no intervention to act as an inactive control.

Note: The employees who volunteer for participation but are assigned to the control condition will be given the opportunity to participate in the exact same program at the completion of the trial with the experimental group. Those employees who take this opportunity can then serve as an internal replication of the findings with the experimental group.

All Participants must meet the following Inclusion/ Exclusion Criteria. Criteria points will be self-reported and acknowledged by the participant.

Key Inclusion Criteria:

- Employed full time by an Atrium Health affiliated entity
- Age 18+
- Willing and able to give written informed consent for study participation.
- Healthcare workers working ≥ 36 hours of clinical duties/week.
- Willingness to wear WHOOP and keep it charged for the entire duration of study.
- Have a smart phone for pairing with WHOOP and the Arena Strive platform.

Key Exclusion Criteria:

- Current diagnosis of a sleep-related breathing disorder including obstructive sleep apnea not being treated (with or without continuous positive airway pressure (CPAP) treatment)
- Circadian rhythm sleep-wake disorders
- Narcolepsy
- Recurrent isolated sleep paralysis
- Restless legs syndrome
- Periodic Leg Movement Disorder
- Comorbid nocturia or other conditions (eg. benign prostatic hyperplasia) resulting in frequent need to get out of bed to use the bathroom during the night (≥ 3 times per night average)
- Atrial Fibrillation
- COPD other than mild, pulmonary fibrosis or severe chronic lung disease
- Sleep apnea or undergoing treatment for a sleep related illness

Last Updated: 2.24.2023

- Lack of availability of iPhone or Android device
- Part-time clinical duties

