2. **Proactive**: Resilience tools and resources are often deployed after an individual or team is already suffering from burnout. Our program is designed to function as a preventative measure upstream of burnout by engaging individuals proactively, though it is also beneficial for those who are already experiencing burnout.
3. **Data-driven**: The Arena Strive platform allows individuals and teams to assess their stress and burnout and evaluate the effectiveness of resilience techniques in real time. De-identified, summarized daily survey and physiologic data can inform organizational interventions and culture change to address drivers of stress and burnout.
4. **Accessible**: The Arena Strive platform is asynchronous and available 24/7 to users regardless of shift, maximizing accessibility to the NHS employees and reducing the barriers associated with accessing traditional resilience training.
5. **Acceptable**: Due to the stigma around help-seeking and mental health diagnoses and a professional culture that has traditionally associated self-care with weakness, healthcare professionals can be hesitant to engage with resilience modalities that are framed as “wellness” or “self-care.” Arena Strive is explicitly framed around the connection between resilience, endurance, and performance and is contextualized to appeal to healthcare professionals.

Participant reimbursement/compensation

Subjects will not receive money, incentives, payment, or reimbursement for participation in this study. Each participant will keep the Whoop device issued to them.

References

1. Shanafelt TD, et al. Changes in Burnout and Satisfaction with Work-Life Integration in Physicians and the General US Working Population Between 2011 and 2017. Mayo Clin Proc. 2019 Sep;94(9):1681-1694.
2. Gualano MR, et al. The Burden of Burnout among Healthcare Professionals of Intensive Care Units and Emergency Departments during the COVID-19 Pandemic: A Systematic Review. Int J Environ Res Public Health. 2021 Aug 2;18(15):8172.
3. Prasad K, et al. Prevalence and correlates of stress and burnout among U.S. healthcare workers during the COVID-19 pandemic: A national cross-sectional survey study. EClinicalMedicine. 2021 May 16;35:100879.

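### No balancing by department is described for the 2:1 allocation and no between-arm analysis has a department term; if work schedule matters, the cost is precision and interpretability, not bias

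*Combined protocol and SAP*

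**What the plan says.** All references are to the combined protocol and SAP.

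- **Who is recruited (Study Participants).** Physicians and Advanced Practice Providers "employed by Atrium Health Sanger Heart and Vascular Institute, Surgery, Emergency Department, and Pulmonary Critical Care". The size is a ceiling: "The maximum number of subjects sought for this study is 100".
- **Allocation (Study Participants).** The only rule is the ratio: "with a 2:1 randomization ratio with 2/3 receiving the experimental intervention, and 1/3 receiving no intervention to act as an inactive control". Study design adds only this: "This study is a prospective randomized controlled longitudinal crossover design with a per protocol analysis". No sequence method, blocking, stratification or minimisation is described anywhere.
- **Work schedule.** Eligibility sets a floor on hours, "Healthcare workers working ≥ 36 hours of clinical duties/week", and no condition on nights or shift type. Shift pattern is not among the variables listed under Data Collection. Shifts are mentioned once, under Benefits, where the platform is called "asynchronous and available 24/7 to users regardless of shift".
- **Analysis (Data Analysis).** Primary outcome measures are compared between arms by t-tests. Sleep, HRV and RHR are compared over time by multilevel models with random intercepts and slopes for individuals. Neither names department, profession or schedule as a term.

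**The concern.** The trial pools emergency, critical care, surgical and heart-and-vascular staff. It is reasonable to suppose, although the documents do not say so, that these groups differ in night and rotating work, and that such work affects sleep consistency, sleep debt, awake time, HRV, RHR and perhaps burnout. The eligibility criteria already treat background sleep disruption as a threat: they exclude circadian rhythm disorders and frequent nocturia. Night work is neither restricted nor recorded.

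Two things would then be at stake. First, variation between departments that could be removed stays in the error term of a small comparison. Second, with about 33 controls the department mix can differ between arms by chance. Several sleep rows would then tend to move together, which could be read as mutual support among endpoints, and without shift data nobody could check afterwards. Department is known for every volunteer before allocation, so using it is easy.

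**Working it through.** **Inputs**

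| Input | Value | Source |
|---|---|---|
| Total N | 100, a maximum | Study Participants |
| Split | 100 × 2/3 = 66.7 and 100/3 = 33.3; 67 and 33 used | Study Participants |
| Share from shift-heavy departments | 40%, varied from 10% to 50% | assumption |
| Schedule effect on an outcome | 0.3 to 1 SD | assumption |

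The plan gives no power calculation, so apart from the split it has no figure to reproduce.

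**Step 1: size of chance imbalance without stratification.** Let x be the number of shift-heavy staff among the 33 controls when 40 of the 100 are shift-heavy. Then x is hypergeometric with mean 33 × 0.4 = 13.2 and variance 33 × 0.4 × 0.6 × 67/99 = 5.36, so SD 2.315. The arm difference in share is

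d = x/33 − (40 − x)/67 = (1/33 + 1/67)(x − 13.2) = 0.0452 (x − 13.2).

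Its SD is 0.0452 × 2.315 = 0.105, or 10.5 points. A difference of at least 15 points needs x ≤ 9 or x ≥ 17; the exact probability is 0.13.

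| Assumed share | SD of d (points) | P(≥10 points) | P(≥15) | P(≥20) |
|---|---|---|---|---|
| 10% | 6.4 | 0.16 | 0.01 | 0.002 |
| 25% | 9.3 | 0.33 | 0.09 | 0.03 |
| 40% | 10.5 | 0.28 | 0.13 | 0.05 |
| 50% | 10.7 | 0.40 | 0.20 | 0.09 |

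The tail probabilities are lumpy because x is a whole number. At 40%, x = 11 gives 9.95 points, just under the 10-point cut. The SD is the steadier guide.

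If four departments are equal in size (assumed), the probability that at least one differs between arms by 15 points or more is 0.28 by simulation. If only 60 are recruited (40 against 20) at a 40% share, the SD is 13.5 points and P(≥15) is 0.40.

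**Step 2: what a 15-point imbalance does to an outcome.** Shift in the arm difference = 0.15 × schedule effect. The standard error of the arm difference, in outcome SDs, is √(1/33 + 1/67) = √0.0452 = 0.213.

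| Schedule effect (SD) | Shift (SD) | Shift ÷ SE |
|---|---|---|
| 0.3 | 0.045 | 0.21 |
| 0.5 | 0.075 | 0.35 |
| 0.8 | 0.12 | 0.56 |
| 1.0 | 0.15 | 0.70 |

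**Step 3: variance left in the error term.** A two-group factor with a 40% share and effect δ, in total SDs, explains R² = 0.4 × 0.6 × δ². For δ = 0.5 this is 0.06; for δ = 1 it is 0.24 (or 0.24/1.24 = 0.19 if δ is in within-group SDs). Removing it multiplies the SE by √(1 − R²): √0.94 = 0.97 and √0.76 = 0.87 (or √0.81 = 0.90). For context, 67 against 33 has about 65% power for a difference of 0.5 SD at an assumed two-sided 0.05, and 80% power needs about 0.60 SD.

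**Step 4: after stratification.** With blocks of 3 in four departments of 25 (assumed), each department has 8 or 9 controls. The largest possible difference in any department's share is 9/33 − 16/67 = 0.273 − 0.239 = 0.034, or 3.4 points.

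**The case against.** The case against is substantial.

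- **The premise is not documented.** A reader might infer that schedule is known to be a strong determinant of these outcomes and known to differ by department. The documents say neither. They give no rosters and no department shares, so both are assumptions here.
- **Silence is not a choice.** A reader might infer that an unstratified list was chosen. The plan states a ratio and no method; a stratified list may exist unreported.
- **Chance imbalance is not bias.** A reader might infer that an excess of night workers in one arm biases the result. Under valid randomisation, such imbalance is already reflected in the t-test's standard error, and overall type I error is not inflated. This stands, with one limit: it covers everyone as randomised, whereas the plan names a per protocol analysis, and exclusions after randomisation could add imbalance that is not random.
- **The size is modest.** Even a 1 SD effect with a 15-point imbalance gives 0.70 of a standard error. This stands.
- **The multilevel models partly deal with it.** If the arm-by-time term is the test, person-level intercepts absorb stable baseline differences. The plan does not name the tested term, nor say whether the t-tests use exit or change scores.
- **Control biometrics are uncertain.** Study design has the sensor worn by those in the experimental intervention, while Data Collection says control data mirror the experimental arm's with a few exceptions. If controls have no sensor data, the point reaches only the survey outcomes.

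What survives is that a known pre-allocation factor appears in neither the described allocation nor the analysis, and that using it costs little.

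**Conclusion.** The point holds as an inexpensive improvement, not as a flaw that invalidates the trial. The documents establish that no balancing by department is described and that no planned between-arm comparison carries a department term. The consequences are conditional on schedule differing by department and affecting the outcomes.

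Under that condition, with 100 randomised and a 40% shift-heavy share, a 15-point imbalance or larger has probability 0.13. A 15-point imbalance shifts an arm difference by about 0.2 to 0.7 of its standard error for schedule effects of 0.3 to 1 SD. The loss is in precision and in how confidently one small trial can be read. The figures do not support a claim of systematic bias or of an inflated false-positive rate.

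**What to change.** 1. **Study Participants:** state the randomisation method, and randomise 2:1 in permuted blocks stratified by department, collapsing small strata.
2. **Data Analysis, t-tests:** for the survey outcomes, replace them with a linear model (ANCOVA) of the exit score on arm, department and the onboarding score. Onboarding scores are already collected, and they adjust for stable differences more directly than department alone.
3. **Data Analysis, multilevel models:** add department as a fixed effect in the between-arm models. This adds least if the arm-by-time term is the test, so name the tested term as well.
4. **If allocation has begun:** enrolment was expected from January 2023 and the document was last updated on 24 February 2023, so this is possible. In that case apply the covariate adjustment alone.
5. **Optional:** one onboarding item on usual night shifts, which would let readers check the assumption made here.

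The cost is a stratified list, a few degrees of freedom and a linear model in place of a t-test. No extra participants are needed.

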Throughout the 12 week intervention period, **participant engagement** within the Arena Strive app will be collected including data points relating to videos/audio watched or listened to, content favorited, or user activities completed. Modifiable activities collected via the Arena Strive Platform include light exposure, light restriction, sleep hygiene, meal timing, and activation and deactivation techniques (yoga nidra, physiological sigh, super O2 breathing).

Self-reported data will also be collected relating to the participants ability to adapt to stress, rest and recover from stress, and self-awareness around these two constructs. WHOOP data, engagement within the Arena Strive app, and self-reported stress adaptability, rest and recovery, and self-awareness will be collected continually throughout the intervention period. The additional self-reported outcomes: professional fulfillment, burnout, self-valuation, and overall satisfaction will be collected by means of an in-app survey at key benchmark moments throughout the intervention period: once at intervention start, again at week 6 following the first phase of the Arena Strive intervention, then again at week 12 following the completion of the experimental intervention period. Participants in the control cohort will follow this same time frame with respect to self-reported surveys. All self-reported data within the control cohort will be collected via identical surveys hosted on Typeform, the web-based surveying platform.

The experimental intervention, 'Arena Strive', will be conducted through the Arena Strive app, self-described as "Healthcare's First Performance Coach". This second-generation platform provides frontline clinicians with a comprehensive journey to access the tools, training, and technology used by other high-pressure fields to increase performance and enhance resilience. Strive uses a dynamic, interactive content platform to bring frontline clinicians the lessons learned, tools, and tailored instruction of world-class performers from elite military, professional athletes, and creative performers. The design will test the effect on measures of professional fulfillment and burnout; self-valuation; satisfaction; and feasibility in full-time NHS clinicians.

Intervention

The experimental intervention employed in this study will be a 12-week, multi-phased approach involving asynchronous learning and coaching experience (6 weeks), and exploration phase (6 weeks).

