As a behavioral intervention, Arena Strive follows the COM-B framework of behavior change, which targets participants' capabilities (C), opportunities (O), and motivations (M) to integrate performance practices into their routines. The first phase of the intervention will involve 6 weeks of micro-learning audio and video content targeting clinicians' capabilities and opportunities to learn and train 17 foundational performance practices. Targeted behavior change techniques (BCTs) help participants overcome barriers, monitor progress, and build intrinsic motivation toward the integration of these 17 practices. These practices leverage techniques and physiological processes that aim to influence the three main foundations of High Performance Medicine: self-awareness, rest & recovery, and stress adaptability. Techniques include but are not limited to autonomic regulation, self-reflection, environmental restructuring, task-based coping, emotion-based coping, guided attention control, and shaping behavior around physiological triggers.

Control Cohort: Participants randomized into the control cohort will receive no intervention for the duration of the experimental intervention. At the conclusion of the full 12 week baseline and intervention period, participants in the control cohort will be given the option to participate in the intervention.

Setting

The study will take place within the Atrium Health Sanger Heart and Vascular Institute, Emergency Department, Surgery and Pulmonary Critical Care.. All data collection, intervention, and participant interaction will take place asynchronously through the Arena Strive smartphone application, and the WHOOP wearable biometric device.

Expected Start Date

The expected enrollment will begin on January 2023 for both cohorts.

Last Updated: 2.24.2023

Duration of Study

The total length of this study will be 24 weeks from participant recruitment to conclusion of data analysis.

- 6 weeks = Phase 1 Enrollment period and participant recruitment, obtain informed consent, complete WHOOP device setup & download Arena Strive app.
- 6 weeks = Phase 2: Arena Strive Intervention period (Arena Strive :: Foundations)
- 6 weeks = Phase 3 Continue WHOOP device & Arena Strive Intervention (Arena Strive :: Explorations)
- 6 weeks = Data analysis

Study Participants

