Participant Consent: All participants involved in this study will be required to provide written consent to participate. Participants will be asked to consent to the collection of self-reported data provided through in-app and digital surveys as well as biometric data collected through the WHOOP device. A copy of the written consent form is included in the appendix. Spanish language consents will be made available upon request.

Equipment/Supplies/Services

All equipment, services, and supplies related to the study intervention will be provided by Arena Labs, and WHOOP. All equipment, services, and supplies related to the recruitment of study participants will be provided by the Atrium Health team.

Data Collection

All study data will be collected via an in-app or online survey, through app interactions, or through the WHOOP wearable biometric device. Data collection for the control cohort will mirror that of the experimental group in both frequency and content with a select few exceptions. Control cohort participants will not receive questions relating to feasibility and satisfaction, and self-reported data will be collected via online surveys hosted on Typeform. A breakdown of the primary and secondary outcome variables are summarized below.

		Outcome Variable	Instrument	Collection Method
Primary Outcomes	Self Reported	Professional Fulfillment & Burnout	Stanford Professional Fulfillment Index (PFI)	Onboard, midpoint, and exit Survey
		"Gold standard" for measuring burnout	Maslach Burnout Inventory (MBI)	Onboard, midpoint, and exit Survey
		Self Valuation	Stanford Self Valuation Scale	Onboard, midpoint, and exit Survey
	Biometric Data	HRV	WHOOP Strap	Continuous
		SWS %	WHOOP Strap	Continuous
		REM %	WHOOP Strap	Continuous
		RHR	WHOOP Strap	Continuous
		Awake Time	WHOOP Strap	Continuous
		Light Sleep Duration (%)	WHOOP Strap	Continuous

		Sleep Disturbances	WHOOP Strap	Continuous
		Sleep Debt	WHOOP Strap	Continuous
		Sleep Consistency	WHOOP Strap	Continuous
Secondary Outcomes	Self-reported	Satisfaction	Client Satisfaction Questionnaire-8 (CSQ-8)	Exit Survey
		Feasibility/Adherence	NA	In-app Survey & app engagement

Data Analysis

- We will use t-tests in SPSS to compare the primary outcome measures across the experimental and control groups.

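### The trial is called a crossover and its opt-in controls an internal replication, but it is a parallel-group trial in which only controls may switch, by choice, after the randomised 12 weeks.

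*Combined protocol and SAP*

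**What the plan says.** Study design describes a "prospective randomized controlled longitudinal crossover design". The Control Cohort paragraph under Intervention gives controls nothing during the experimental period; once the 12 weeks are over, "participants in the control cohort will be given the option to participate in the intervention". Study Participants sets a maximum of 100 people randomised 2:1 and offers volunteers assigned to control the "exact same program at the completion of the trial with the experimental group". It then states the use to be made of them: "Those employees who take this opportunity can then serve as an internal replication of the findings with the experimental group".

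Duration of Study says: "The total length of this study will be 24 weeks from participant recruitment to conclusion of data analysis". It lists four blocks of six weeks: enrolment, Foundations, Explorations and data analysis.

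Data Analysis begins: "We will use t-tests in SPSS to compare the primary outcome measures across the experimental and control groups". It goes on to dose-effect correlations and dose-effect multilevel models within the experimental condition, a multilevel model of sleep, HRV and RHR over time by condition, and mediation models. None of these names the data that controls would supply after opting in, and no criterion for a successful replication is given.

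**The concern.** A crossover label tells the reader that participants receive both conditions in randomised order, so that within-person contrasts carry the protection of randomisation. Nothing of that kind happens here. A replication claim tells the reader that the same effect has been estimated again by a comparable method. After week 12 that is not possible, because everyone still untreated has either chosen to start or chosen to decline, and the experimental arm has already had the programme.

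If the text is followed as written, a non-randomised change in volunteers could be reported as confirming a randomised result. The multilevel model also names no time limit, so nothing in the text keeps opt-in data out of it.

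**Working it through.** **Does the design have the parts of a crossover?**
- *Both arms switch:* no. Only controls are offered a change of condition; the experimental arm is never moved to a control condition.
- *Order of conditions randomised:* no. The single possible order is control then programme, and it is taken by choice.
- *Washout, period or carryover terms:* none is mentioned in the design or analysis sections.

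What remains is a 2:1 parallel comparison over 12 weeks, then optional access for controls.

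**How many people could the replication include?** Maximum 100 at 2:1 gives 100 × 2/3 ≈ 67 experimental and 100/3 ≈ 33 control. The ceiling is therefore about 33, at full uptake. The documents give no expected uptake.

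**What would the opt-in change estimate?** Let Y0, Y12 and Y24 be an opt-in's scores at the start, at the end of the control period and at the end of their own programme. The before-after change is Y24 − Y12. It contains the programme effect plus any time trend, and no concurrent randomised group is left from which to estimate that trend.

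The decision to join is also made around week 12. Suppose people tend to join when their week-12 score is, by chance, e above their usual level. Then, with no programme effect and no trend:
- expected Y24 − Y12 = −e
- expected Y12 − Y0 = +e
- expected difference between the two changes = −e − e = −2e

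So setting each person's programme period against their own control period does not remove the selection problem. The shared week-12 score enters both changes with opposite sign.

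**Is there time for it in the schedule?** The stated total reproduces: 6 + 6 + 6 + 6 = 24 weeks. On that clock the randomised period ends at 6 + 12 = 18 weeks and analysis runs from week 18 to week 24. A control who started at week 18 would be six weeks into a 12-week programme when the planned analysis closes. With the opt-in programme placed before analysis, the total is 6 + 12 + 12 + 6 = 36 weeks.

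**Would control-period data exist for every outcome?** Nine of the twelve primary outcome rows in the Data Collection table are WHOOP measures. Study design describes the sensor as worn by participants in the experimental intervention. Data Collection says control data mirror those of the experimental group apart from a few exceptions, and the sensor is not among the exceptions it lists. The two sections do not settle whether controls have sensor data before they opt in.

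**The case against.** The best defence is that little depends on these words. The replication sentence is permissive and sits in a note; it is not an objective, an outcome or a listed analysis. The sections on the control cohort and on participants say plainly who gets what and when, and no listed analysis uses crossover methods. This stands to the extent that no planned estimate is wrong because of the label. It does not rescue the sentence, which is the only stated use of the opt-in data and claims a property that those data lack.

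It can also be said that the findings to be replicated are the experimental arm's own trajectory or dose effects, not the between-arm difference. The wording allows that. But a similar trajectory in volunteers would still be uncontrolled, and would not confirm efficacy.

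Four stronger readings are tempting, and the documents do not support them:
- *The randomised comparison is compromised.* It is not, on this point: controls receive no programme during the 12 weeks.
- *The plan intends to pool opt-in data in the multilevel model.* The text is silent. The survey schedule stops at week 12, and complete opt-in data could not exist in the planned analysis window. The gap needs one sentence; it is not evidence of intent.
- *The 24-week total is an error.* It adds up, and it is consistent if the opt-in phase lies after the trial. It needs restating only if opt-in data are to be reported.
- *The opt-in data are simply too imprecise.* Precision is not the flaw. Assume full uptake, complete data and a between-visit correlation of 0.6, none of which comes from the documents. The SD of a change is then √(2 × 0.4) = 0.894 SD. The 95% half-width is 2.037 × 0.894/√33 = 0.317 SD for the simple before-after change in 33 people, and 1.984 × 0.894 × √(1/67 + 1/33) = 0.377 SD for the randomised comparison of changes. The uncontrolled figure can look the more precise of the two, which makes its label matter more.

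**Conclusion.** The concern holds for the design label and for the replication claim. Both assert properties the design does not have. The trial is a randomised parallel-group study with optional delayed access for controls, and its opt-in phase can yield only a non-randomised, uncontrolled change in at most about 33 self-selected people.

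The damage is limited to that secondary claim. The 12-week comparison is unaffected here so long as opt-in data stay out of it. The absence of a named opt-in analysis would, alone, be only missing detail; it matters because the text gives those data a confirmatory role.

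The conclusion follows from the wording and from the 2:1 ratio at the stated maximum of 100. It does not rest on any assumed uptake, correlation or effect size. The size of the bias from selection, trend or regression to the mean cannot be estimated from the documents.

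**What to change.** 1. In Study design, replace the crossover label with *randomised parallel-group trial with optional delayed access for controls*.
2. In Data Analysis, confine efficacy conclusions to the randomised 12 weeks, and state that the multilevel model comparing conditions uses only those weeks.
3. In Study Participants, replace the replication claim with *exploratory, non-randomised follow-up of controls who opt in*.
4. If opt-in data are to be reported:
   - show each opt-in's programme-period change beside their own control-period change, with 95% confidence intervals for the two mean changes;
   - do this for WHOOP measures only if control-period sensor data exist, and reconcile Study design with Data Collection on that;
   - give the number opting in and the week-12 scores of opt-ins and decliners, so that selection at week 12 can be seen;
   - restate the duration as about 36 weeks (6+12+12+6).

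Items 1 to 3 cost only wording. Item 4 adds 12 weeks of the existing surveys, sensor data from both periods if WHOOP outcomes are included, and a later end date. The downside in either case is a weaker secondary claim: the opt-in data can no longer be cited as confirmation.
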